### **7.3.1 Inclusion Criteria**

Subjects must meet all of the following criteria to be eligible for the study:

1. Men or non-pregnant or non-breastfeeding women over 21 years of age
2. If female and of childbearing potential, a negative urine pregnancy test at Baseline (Day 1) and the subject agrees to use adequate contraception during the study period

3. Has an overall score of very thin or thin on the LFGS, as agreed upon by the Treating and Evaluating Investigators, and desires at least a 1-point improvement in overall LFGS score; OR  
Has a Fitzpatrick skin phototype IV, V or VI and has an LFGS score of thick or full, as agreed upon by the Treating and Evaluating Investigators, and desires treatment to the vermilion body of 1 or both lips
4. Willing to give written informed consent

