### 8.2 Efficacy Analysis

The primary efficacy endpoint is change from baseline to Month 2 in overall lip fullness based on the Blinded Evaluating Investigator assessment using the LFGS. A 95% confidence interval (CI) will be constructed for the difference between PN40082 and Restylane Silk (i.e. PN40082 minus Restylane Silk) with respect to the primary endpoint. If the lower limit of this 95% CI is above a pre-specified NI limit - 0.50, PN40082 will be claimed non-inferior to Restylane Silk.

The primary endpoint will also be analyzed for the following two subsets of subjects: (1) subjects that have injection on one lip only, and (2) subjects that have injections on both lips.

Secondary analysis include

- percent of subjects with treatment success (responder: overall LFGS based on the Blinded Evaluating Investigator Assessment) at Visit 3/Month 2 where responder is defined as a subject with at least a 1-grade increase from baseline on the LFGS post augmentation,
- percent of responders overall on the POL severity scale at Visit 4/Month 3 (defined as a subject demonstrating  $\geq 1$ -point improvement, i.e., decrease in severity, from baseline),
- change from baseline to Visit 4/Month 3 in overall LFGS based on the Blinded Evaluating Investigator Assessment
- change from baseline to Visit 5/Month 6 in overall LFGS based on the Blinded Evaluating Investigator Assessment.

For this non-inferiority study, the null hypothesis to be tested for all the secondary endpoints is that there is no difference between the two products, and all statistical comparisons for these endpoints will be considered descriptive (non-inferential). These secondary variables will be summarized with descriptive statistics for

each treatment arm and a 95% CI for the difference between treatments. For the proportion variables, the 95% CI for treatment difference will be calculated using the Wald's method, with subjects pooled from all study sites. For the change variables, the 95% CI for treatment difference will be derived using ANCOVA with factors of treatment and site, and the corresponding baseline value for the endpoint as covariate.

Other efficacy analysis include

- pGAI, iGAI, and Swelling Assessment at each scheduled visit,
- percent of subjects with treatment success (responder: upper lips, lower lips LFGS) at Visit 3/Month 2 where responder is defined as a subject with at least a 1-grade increase from baseline on the LFGS post augmentation,

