### **8.5 Sample Size Determination**

For the PRO 2018-02 study, the primary variable is change from baseline to Month 3 in LFGS. The sample size was determined based on (1) both PN40082 and Restylane Silk having an equal mean value with a common standard deviation of 0.85 for change from baseline in LFGS, and (2) the non-inferiority limit of -0.50. The test:control ratio of 1:1 results in 126 (63:63) PP subjects at 90% power. Assuming 80% of randomized subjects meet the PP criteria, a total of 158 (79:79) subjects will be randomized to obtain 126 (63:63) PP subjects.

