3.2 Sample Size Determination

For the PRO 2018-02 study, the primary variable is change from baseline to Month 3 in LFGS. The sample size was determined based on: (1) both PN40082 and Restylane Silk having an equal mean value with a common standard deviation of 0.85 for change from baseline in LFGS, and (2) the non-inferiority limit of -0.50. The test:control ratio of 1:1 results in 126 (63:63) per-protocol (PP) subjects at power of 90%. A total of 158 subjects will be randomized to obtain 126 (63:63) PP subjects assuming that 80% of randomized subjects meet the PP criteria.

4 Populations To Be Analyzed

Three subject populations are defined as follows:

- (1) As-treated (AT) (safety population): All randomized subjects who received study device. AT subjects will be included in the safety analysis for the treatment they actually received.
- (2) Modified intent-to-treat (mITT): All randomized subjects who met the inclusion/exclusion criteria, and received study device.
- (3) Per-protocol (PP): All randomized subjects who met all inclusion/exclusion criteria; received study device; completed Visit 5/Month 6 within the specified window; had overall LFGS score by the Blinded Evaluating Investigator at Visit 3/Month 2 within the specified visit window; and had no significant protocol violations that would affect the treatment evaluation.

For the purpose of determining the PP status of the subject, "significant protocol violations" are any unforeseen events that occurred during the conduct of the trial that result in noteworthy study protocol violations that could have possibly interfered with the therapeutic administration of the treatment or the precise evaluation of treatment efficacy.

Efficacy analyses will be performed on the mITT and PP populations, with PP as the primary population and mITT supportive. Analyses of safety and other evaluations will be performed on the AT population.

5 Planned Analyses

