5.5.1 Primary Efficacy Analysis

The primary efficacy endpoint is change from baseline to Visit 3/Month 2 in overall LFGS. The null hypothesis to be tested is that the Test device is inferior to the Control device. The results for PP are considered as definitive and those for mITT as supportive.

Summary statistics (mean, SD, minimum, median, maximum) and 95% confidence interval (CI) for mean will be presented for the changes scores for each treatment.

Due to the fact that the change scores would only contain 5 possible values (0, 1, 2, 3, and 4), the normal distribution assumption is hardly attainable, and therefore, the nonparametric Hodges-Lehmann (HL) estimators will be employed to test the study hypothesis. The 95% confidence limits for the median differences between the two treatment groups (PN40082 minus Restylane Silk) will be derived using PROC NPARIWAY with the option for the HL estimators. If the lower limit is on or above -1.0, the null hypothesis will be rejected to support the claim that PN40082 is non-inferior to Restylane Silk.

For the mITT analysis, the above analysis will be carried out for each copy of the MI data sets. Then PROC MIANALYZE will be performed to account for the between and within variation in the multiply imputed data sets.

To assist an assessment for the consistency of the treatment effect among sites, summary of the primary endpoint will be presented by site for the primary population (i.e., the PP subjects).

The primary endpoint will also be analyzed for the following two subsets of the PP subjects: (1) subjects that have injection on one lip only, and (2) subjects that have injections on both lips.

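### The primary Hodges-Lehmann interval often collapses to a point and does not track the mean difference used for sizing; a supportive baseline- and site-adjusted ANCOVA would report that difference

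*SAP*

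**What the plan says.** SAP 5.5.1 takes change in overall LFGS from baseline to Month 2 as the primary endpoint. It gives non-normality of a short whole-number score as the reason why "the nonparametric Hodges-Lehmann (HL) estimators will be employed to test the study hypothesis". The limits for the median difference "will be derived using PROC NPARIWAY with the option for the HL estimators". No covariate or stratum is named. Baseline enters only by subtraction, and site only through a by-site summary. The decision rule is: "If the lower limit is on or above -1.0, the null hypothesis will be rejected". SAP 1 attributes the rank method to FDA comments about ties.

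The sizing is on means. Protocol 8.5 and SAP 3.2 assume equal means, a "common standard deviation of 0.85 for change from baseline in LFGS" and "the non-inferiority limit of -0.50".

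For the secondary change endpoints, Protocol 8.2 says the interval is "derived using ANCOVA with factors of treatment and site, and the corresponding baseline value for the endpoint as covariate". It names no model for the primary endpoint. SAP 5.5.2 replaces that ANCOVA with Hodges-Lehmann (HL) for the secondary endpoints too.

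Protocol 7.3.1 admits subjects with very thin or thin lips (grades 0-1), or a subject with Fitzpatrick type IV-VI who "has an LFGS score of thick or full" (grades 3-4). The scale ends at 4 (Protocol 7.6.9).

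**The concern.** Two features of the primary analysis limit what it can tell the reader.

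First, every pairwise difference between whole-number scores is a whole number. The HL estimate and its limits therefore move in steps of one grade, while the effect the trial was sized to exclude is half a grade. An interval reported as 0 to 0 says little about how far the mean difference lies from -0.50.

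Second, a subject who starts at 4 cannot gain and one who starts at 3 can gain at most one grade, whereas a subject at 0 or 1 has three or four grades of room. Baseline is therefore related to change whenever thick/full subjects are enrolled. Baseline and site are both collected and both stand in the imputation model (SAP 5.2), but neither is used to sharpen the primary comparison.

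At stake are the precision and readability of the main result, and whether the report contains the quantity on which the sample size was justified.

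**Working it through.** **1. The plan's own figure.** Inputs from Protocol 8.5: margin 0.50, SD 0.85, true difference 0, 90% power, two-sided 95% CI (one-sided 0.025).

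n per arm = 2 × 0.85² × (1.960 + 1.282)² / 0.50² = 60.7, so 61; the t version gives 62. The plan has 63. At 63 per arm, SE = 0.85 × √(2/63) = 0.151, and power = Φ(0.50/0.151 − 1.96) = 91.0% (90.6% with t). 126/0.80 = 157.5, so 158. The sizing reproduces as a comparison of means.

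**2. Where the HL limits fall.** There are 63 × 63 = 3,969 pairwise differences. The large-sample lower position is 3969/2 − 1.96 × √(3969 × 127/12) = 1984.5 − 401.7 = 1582.8, or 39.9% of the way up the ordered differences. The upper position is at 60.1%. The interval is [0, 0] unless about 40% of the differences are below zero or about 40% are above it.

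**3. How often the width is zero.** Simulated whole-number changes (rounded normal, an assumed shape), 63 per arm:

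| True mean difference (observed SD about 0.865) | Zero width | Average HL estimate |
|---|---|---|
| 0 | 77% | 0.00 |
| -0.1 | 67-69% | -0.01 |
| -0.2 | 47-48% | -0.03 |
| -0.3 | 24-26% | -0.11 |
| -0.4 | 10-11% | -0.26 |
| -0.5 | 5-6% | about -0.50 |
| -0.6 | about 11% | -0.73 to -0.74 |
| -0.75 | 36-38% | about -0.95 |
| -1.0 | 77-78% | -1.00 |

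With equal arms and an observed SD of 0.82-0.87 the share is 73-81%. With scores capped at 4 and 0-30% thick/full subjects it is 72-81%. Over SDs of 0.69 to 1.07 it runs from 96% down to 38%. At intermediate true differences the usual result is [-1, 0]. The average estimate agrees with the mean difference near 0, -0.5 and -1, and departs from it between them.

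**4. The mean-difference interval.** At SD 0.85 its half-width is 1.96 × 0.151 = 0.30. In equal-arm simulations with capped scores, t-interval coverage was 94.5-95.3%, so non-normality at 63 per arm is not a reason to omit it.

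**5. What adjustment adds, against an unadjusted mean-difference test at -0.50.** By formula, residual SD = 0.85 × √(1 − R²). R² values of 0, 0.1, 0.2 and 0.3 give power at 63 per arm of 91.0%, 93.6%, 95.8% and 97.6%. The documents give no R², so it was generated from capped 0-4 scores with no site differences:

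| Thick/full share | Unadjusted to baseline + 7 sites | Unadjusted to baseline only |
|---|---|---|
| 0% | 92.3% to 90.9% | 92% to 91% |
| 10% | 89.6% to 91.1% | 91% to 94% |
| 20% | 89.7% to 93.8% | 89% to 95% |
| 30% | 87.6% to 94.7% | 89% to 96% |

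A less favourable assumed shape gave 89.4% to 92.3% at 20%. A smaller assumed average gain (1.2 grades before the cap, baseline + 7 sites) gave 90.6% to 94.4% at 30%. With 2,000 runs the simulation error is about √(0.9 × 0.1/2000) = 0.7 points. Real site differences would add to the gain: with an assumed between-site SD of 0.5 and no thick/full subjects, power goes from 85.8% to 91.2%.

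**The case against.** The strongest reply is that the point-like interval hardly alters the decision. Tested at -0.50, the HL interval passes in 88-89% of trials at equality and 2.7-2.9% at a true difference of -0.5; the t interval passes in 89-90% and 2.3-2.8%. That stands. A reader might infer that zero width makes the test lenient. It does not: the leniency comes from the inclusive -1.0 limit, at which about 100% of trials pass at a true mean difference of -0.5 or -0.6, and 88-89% at -1.0. That is a separate conflict.

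Second, the method follows FDA comments, and the SAP already tabulates each arm's mean with its CI, baseline LFGS by arm, by-site results and a responder difference with a CI. All true. However, no table shell gives a CI for the difference in means, and a reader should not have to construct one.

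Third, the gain rests on a thick/full share that the protocol does not set. Also true. The nearest figure in the documents is the comparator cannula study, where six of 60 subjects (10%) were exempt from the lip-score criterion. The gain is therefore given as a range that starts at nil.

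A reader might also infer that the unadjusted comparison is biased, or that chance imbalance in thick/full subjects threatens the SAP's result. Randomization rules out systematic bias. With 16 versus 10 such subjects, simulation shifted the mean by -0.07, but the HL estimate stayed at 0 in 99.6% of runs and the SAP rule still passed in every run. Nor did the protocol promise ANCOVA for the primary endpoint; it names it only for the secondary change endpoints.

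**Conclusion.** The point holds as one of reporting and precision. Under the sponsor's planning case the primary interval will have zero width in roughly 70-80% of trials, less often if the true difference is about -0.2 to -0.75. The estimate does not track the mean difference used for sizing, and the SAP plans no confidence interval for that difference. Omitting baseline costs precision. Relative to an unadjusted mean test the recoverable power is nil with no thick/full subjects, about 1-3 points at 10%, 3-6 at 20% and 4-7 at 30%. If baseline and site carry no signal, adjustment costs about one point.

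These gains are not gains over the SAP's own rule, under which equal arms pass about 100% of the time at -1.0. They rest on assumed score shapes, an assumed thick/full share and no site differences.

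**What to change.** Keep the HL analysis as planned. Add to SAP 5.5.1, before unblinding, a supportive ANCOVA of the Month 2 change in overall LFGS with treatment, site and baseline LFGS, reporting the adjusted mean difference and its 95% CI beside -0.50. Restoring the same model for the secondary change endpoints would bring SAP 5.5.2 back in line with Protocol 8.2.

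The cost is one model and one row in Table 14.2.1.1, with no new data. Do not require the two analyses to agree before non-inferiority is claimed: that would be a new success criterion, would lower the chance of success at equality from about 100% under the SAP rule to about 90%, and would need its own justification and discussion with the FDA.

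Separately, reconcile the -1.0 limit in SAP 5.5.1 with the -0.50 in Protocol 8.2 and in both sizing sections. The supportive analysis does not settle that conflict.

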**Efficacy Analysis:**

The primary efficacy endpoint is change from baseline to Month 2 in overall lip fullness based on the Blinded Evaluating Investigator assessment using the LFGS. If the lower limit of the 95% confidence interval (CI) for (PN40082 minus Restylane Silk) with respect to the primary endpoint is above a pre-specified NI limit -0.50, PN40082 will be claimed non-inferior to the Restylane Silk.

Secondary analysis include

- percent of subjects with treatment success (responder: overall LFGS based on the Blinded Evaluating Investigator Assessment) at Visit 3/Month 2 where responder is defined as a subject with at least a 1-grade increase from baseline on the LFGS post augmentation,
- percent of responders overall on the POL severity scale at Visit 4/Month 3 (defined as a subject demonstrating  $\geq 1$ -point improvement, i.e., decrease in severity, from baseline),
- change from baseline to Visit 4/Month 3 in overall LFGS based on the Blinded Evaluating Investigator Assessment,
- change from baseline to Visit 5/Month 6 in overall LFGS based on the Blinded Evaluating Investigator Assessment.

Other efficacy analysis include

- pGAI, iGAI, and Swelling Assessment at each scheduled visit,
- percent of subjects with treatment success (responder: upper lips, lower lips LFGS) at Visit 3/Month 2 where responder is defined as a subject with at least a 1-grade increase from baseline on the LFGS post augmentation,
- percent of responders (upper lips, lower lips) on the POL severity scale at Visit 4/Month 3 (defined as a subject demonstrating  $\geq 1$ -point improvement, i.e., decrease in severity, from baseline),
- satisfaction with lips VAS at each scheduled visit,
- change from baseline to Visit 4/Month 3 and Visit 5/Month 6 in upper lips, lower lips LFGS.

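### The SAP's primary decision rule accepts a lower limit of -1.0, against the protocol's and the SAP's own design margin of -0.50, so a device one full grade worse would usually be declared non-inferior

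*SAP*

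**What the plan says.** **Protocol.** The synopsis gives the rule for the lower 95% limit of PN40082 minus Restylane Silk: if it "is above a pre-specified NI limit -0.50, PN40082 will be claimed non-inferior to the Restylane Silk". Section 8.2 repeats this ("If the lower limit of this 95% CI is above a pre-specified NI limit"), again with -0.50. Section 8.5 sizes the trial on the same limit.

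**SAP 3.2.** The sample size rests on "the non-inferiority limit of -0.50" and on "both PN40082 and Restylane Silk having an equal mean value with a common standard deviation of 0.85 for change from baseline in LFGS". It gives 63 per-protocol subjects per arm at 90% power.

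**SAP 5.5.1.** The estimator becomes Hodges-Lehmann and the rule becomes: "If the lower limit is on or above -1.0, the null hypothesis will be rejected to support the claim that PN40082 is non-inferior". The per-protocol result under this rule is the definitive one.

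**Reasons given.** SAP section 1 attributes the Wilcoxon/Hodges-Lehmann method to FDA comments about tied ranks, and 5.5.1 adds that the change scores will not be normal. Both reasons concern the estimator. Neither document gives a reason for moving the limit from -0.50 to -1.0, or for counting the boundary as a pass.

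**The concern.** The SAP states that it implements section 8 of the protocol, yet it decides the primary hypothesis at twice the protocol's margin and replaces a strict inequality with one that includes the boundary. On a whole-grade scale the second change matters as much as the first, because the boundary value -1 is one that the lower limit will often take.

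One grade is also the trial's own responder threshold (SAP 5.5.2), so the rule lets the test device lose a whole responder step and still succeed. The one-sided 2.5% error rate implied by the protocol's interval at -0.50 is no longer controlled. The stated 90% power belongs to a comparison of means at -0.50, not to the test that will be run.

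**Working it through.** **1. Reproduce the plan's sample size.** Inputs from SAP 3.2: margin 0.50, SD 0.85, true difference 0, 90% power. A two-sided 95% interval gives one-sided 2.5%.

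n per arm = 2 × (1.960 + 1.282)² × 0.85² / 0.50² = 60.7, so 61 (62 with the t distribution). The plan's 63 per arm gives 90.6% power (t), and 126 / 0.80 = 157.5, so 158. The figures reproduce from -0.50. With a margin of 1.0 the same formula gives 15.2, so 16 per arm. The design margin is therefore -0.50.

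**2. What the SAP rule means on whole grades.** The Hodges-Lehmann lower limit is an ordered value among the m × n pairwise differences. With m = n = 63 there are 3,969 differences, and the rank is

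mn/2 − 1.96 × √(mn(m+n+1)/12) = 1984.5 − 1.96 × √(3969 × 127 / 12) = 1984.5 − 401.7 = 1582.8.

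Every difference is a whole number, so the limit is one too. A limit at or above -1.0 means -1, 0, 1 and so on, and only -2 or lower fails. A limit above -0.50 means 0 or more.

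**3. An example without a distributional assumption.** Suppose all 63 test subjects have no change, while 38 controls gain one grade and 25 gain two. Then 63 × 25 = 1,575 differences equal -2 and 63 × 38 = 2,394 equal -1. Rank 1,582 or 1,583 falls among the -1 values, so the lower limit is -1 and the SAP rule declares non-inferiority. Yet responders are 0% against 100%, and the mean difference is −(38 + 50)/63 = −1.40.

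**4. How often a worse device passes.** Simulation, 63 per arm, integer changes made by rounding a normal variable, control mean gain 1.2 to 2.0 grades. The wider range varies the observed SD from about 0.75 to 1.04 and includes runs with changes confined to 0-4. Dashes mark cells that were not computed.

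| True mean difference | SAP rule, SD about 0.85 | SAP rule, wider range | Hodges-Lehmann above -0.50 | Mean-difference CI above -0.50 |
|---|---|---|---|---|
| 0 | 100% | 100% | about 90% (75-96%) | 90-92% |
| -0.50 | 100% | 99.9-100% | 2-3% | 2-3% |
| -0.75 | 99.7-99.9% | 97.5-100% | under 0.1% | – |
| -1.00 | 89-91% | 74-99% | 0.0% | about 7 × 10⁻⁸ |
| -1.25 | 36-42% | 22-51% | 0.0% | – |
| -1.50 | 3-5% | 1-3% | 0.0% | – |

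The last-column entry at -1.00 is analytic. SE = 0.85 × √(2/63) = 0.151. A pass needs an estimate above −0.50 + 1.96 × 0.151 = −0.203, which is 5.26 standard errors from −1.00.

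**5. Which feature does the damage.** The value -1.0, the included boundary and the whole-grade scores act together. A mean-based interval with margin -1.0 would pass a one-grade-worse device only 2.5% of the time. On integer limits, a strict rule above -1.0 would act exactly like one above -0.50.

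**The case against.** No one can argue that the texts agree. The best case on the other side concerns degree.

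- **The margin may have been discussed with the regulator.** SAP section 1 names two FDA points in particular, which need not be a complete list, and that correspondence is not available here. So the change cannot be called an oversight. It remains unexplained, and SAP 3.2 contradicts SAP 5.5.1 within one document.
- **The rule does reject poor products.** About 60% of devices 1.25 grades worse fail, and nearly all that are 1.5 grades worse. This stands. The accurate description is an effective margin near -1.5, not a rule that rejects nothing.
- **The 89-91% figure depends on an assumed shape.** This also stands. Over the other shapes and SDs tried it is 74-99%, and usually passing is a fair description throughout.
- **Power under the restored margin may fall short of 90%.** It is about 90% at the planned SD but 75% at SD 1.04. Inclusion criterion 3 also admits subjects with thick or full lips, who can gain at most one grade or none. If 10-30% of subjects were of this kind (an assumption, since the documents give no proportion), power at equality was about 83-87%. This is a caveat on power and no argument for a looser margin.
- **The pooled mITT interval need not be a whole number.** True, but that analysis is only supportive.

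**Conclusion.** The concern holds. SAP 5.5.1 contradicts the protocol's decision rule and SAP 3.2, and the rule it sets is far looser than -1.0 suggests. At the planned SD it declares non-inferiority for a device one grade worse in about 90% of trials, and at the protocol margin itself essentially always. The effective margin is about -1.5, three times the -0.50 on which the trial was sized.

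The textual conflict and the example in step 3 need no distributional assumption. The pass rates rest on rounded-normal change scores, the assumed control gain and SD, and the large-sample Hodges-Lehmann limit without a tie correction. A tie correction would narrow the interval and could only raise the pass rates.

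This rule decides the primary claim, so it must be corrected before unblinding.

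**What to change.** 1. In SAP 5.5.1, require the lower 95% limit to be strictly above -0.50, as in protocol 8.2 and SAP 3.2. Keep Hodges-Lehmann, state that its limits are whole numbers so that the rule means a lower limit of at least 0, and report the 95% interval for the mean difference beside it.
2. If a margin of -1.0 is truly intended, justify it, state whether the boundary passes and what that means on whole-grade data, and amend protocol 8.2, the synopsis and both sample size sections before unblinding.
3. In protocol 8.5 and SAP 3.2, correct the time point ("the primary variable is change from baseline to Month 3 in LFGS"), since the primary endpoint is at Month 2, and tie the 90% power to the rule that will be used. This is a separate slip and adds no weight to the main point.

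The first remedy costs wording only. With 63 per arm and SD 0.85, simulated power at equality stays at about 90%. The false-claim rate at -0.50 is about 2-3%, and up to 5% in one set of runs with changes confined to 0-4. The SAP should acknowledge the lower power that would follow from a larger SD or from many subjects with full lips at baseline.
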